4.2.2.3 Contraception requirements

If female subjects of child-bearing potential are included in the trial, adequate contraception is to be maintained throughout the course of the trial (see Section [3.3.2](#) for the definition of adequate measures).

4.3 TREATMENT COMPLIANCE

Compliance will be assured by administration of all trial medication in the trial centre under supervision of the investigating physician or a designee. The measured plasma concentrations of trial medication will provide additional confirmation of compliance.

Subjects who are non-compliant (for instance, who do not appear for scheduled visits or violate trial restrictions) may be removed from the trial and the CRF will be completed accordingly (for further procedures, please see Section [3.3.4.1](#)).

5. ASSESSMENTS

5.1 ASSESSMENT OF EFFICACY

Not applicable.

5.2 ASSESSMENT OF SAFETY

5.2.1 Medical examination

At screening, the medical examination will include demographics, height and body weight, smoking and alcohol history (alcohol history not mandatory to be entered into CRF or to be reported), relevant medical history and concomitant therapy, review of inclusion and exclusion criteria, review of vital signs (BP, PR), 12-lead ECG, laboratory tests, and a physical examination. At the end of trial examination, it will include review of vital signs, 12-lead ECG, laboratory tests, and a physical examination.

Suicidality assessment (see section [5.2.5.1](#)) is performed at the timepoints indicated in the [Flow Chart](#).

5.2.2 Vital signs

Systolic and diastolic blood pressures (BP) as well as pulse rate (PR) or heart rate (heart rate is considered to be equal to pulse rate) will be measured by a blood pressure monitor (Dinamap Pro 100, [REDACTED]) at the times indicated in the Flow Chart, after subjects have rested for at least 5 min in a supine position. All recordings should be made using the same type of blood pressure recording instrument on the same arm, if possible.

5.2.3 Safety laboratory parameters

For the assessment of laboratory parameters, blood and urine samples will be collected by the trial site at the times indicated in the Flow Chart after the subjects have fasted for at least 9 h. For retests, at the discretion of the investigator or designee, overnight fasting is not required.

The parameters to be assessed are listed in Tables [5.2.3: 1](#) and [5.2.3: 2](#). Reference ranges will be provided in the ISF.

Manual differential white blood cell count or urine sediment examinations will only be performed if there is an abnormality in the automatic blood cell count or in the urinalysis, respectively.

[REDACTED]

Proprietary confidential information © 2022 Boehringer Ingelheim International GmbH or one or more of its affiliated companies

Table 5.2.3: 1

Routine laboratory tests

Functional lab group	BI test name [comment/abbreviation]	A	B	C
Haematology	Haematocrit Haemoglobin Red Blood Cell Count/Erythrocytes White Blood Cells/Leucocytes Platelet Count/Thrombocytes (quant) Erythrocyte Sedimentation Rate 1 h	X X X X X X	X X X X X X	X X X X X X
Automatic WBC differential, relative	Neutrophils/Leukocytes; Eosinophils/Leukocytes; Basophils/Leukocytes; Monocytes/Leukocytes; Lymphocytes/Leukocytes	X	X	X
Manual differential WBC (if automatic differential WBC is abnormal)	Neut. Poly (segs)/Leukocytes; Neutrophils Bands/Leukocytes; Eosinophils/Leukocytes; Basophils/ Leukocytes; Monocytes/Leukocytes; Lymphocytes/Leukocytes			
Coagulation	Activated Partial Thromboplastin Time Prothrombin time Prothrombin time – INR (International Normalization Ratio)	X X X	-- -- --	-- -- --
Enzymes	AST [Aspartate aminotransferase] /GOT, SGOT ALT [Alanine aminotransferase] /GPT, SGPT Alkaline Phosphatase Gamma-Glutamyl Transferase Creatine Kinase [CK] Creatine Kinase Isoenzyme MB [only if CK is elevated]	X X X X X X	X X X X -- --	X X X X -- --
Hormones	Thyroid Stimulating Hormone	X	--	--

Substrates	Glucose (Plasma) Creatinine GFR/ CKD-EPI Bilirubin, Total Bilirubin, Direct Protein, Total C-Reactive Protein (Quant)	X X X X X X	X X X X X X	X X X X X X
------------	---	----------------------------	----------------------------	----------------------------

* In male subjects only

Table 5.2.3: 1

Routine laboratory tests (cont.)

Functional lab group	BI test name [comment/abbreviation]	A	B	C
Electrolytes	Sodium Potassium	X X	X X	X X
Urinalysis (Stix)	Urine Nitrite (qual) Urine Protein (qual) Urine Glucose (qual) Urine Ketone (qual) Urobilinogen (qual) Urine Bilirubin (qual) Urine RBC/Erythrocytes (qual) Urine WBC/Leucocytes (qual) Urine pH	X X X X X X X X	-- -- -- -- -- -- -- --	X X X X X X X X
Urine sediment (microscopic examination if erythrocytes, leukocytes nitrite or protein are abnormal in urine)	Only positive findings will be reported (for instance, the presence of sediment bacteria, casts in sediment, squamous epithelial cells, erythrocytes, leukocytes)			

A: parameters to be determined at Visit 1 (screening examination)

B: parameters to be determined at Visit 2, 3, 4 and 5 (for time points refer to [Flow Chart](#))

C: parameters to be determined at Visit 6 (end of trial examination)

The tests listed in Table [5.2.3: 2](#) are exclusionary laboratory tests that may be repeated as required. The results will not be entered in the CRF/database and will not be reported in the CTR. Except for pregnancy tests and drug screening, it is planned to perform these tests during screening only. Pregnancy testing in women will be performed at screening, prior to each treatment period, and as part of the end of trial examination. Drug screening will be performed at screening and prior to each treatment period.

Table 5.2.3: 2 Exclusionary laboratory tests

Functional lab group	Test name
Drug screening (urine)	Amphetamine/MDA Barbiturates Benzodiazepine Cannabis Cocaine Methadone Methamphetamines/MDMA/Ecstasy Opiates Phencyclidine Tricyclic antidepressants
Infectious serology (blood)	Hepatitis B surface antigen (qualitative) Hepatitis B core antibody (qualitative) Hepatitis C antibodies (qualitative) HIV-1 and HIV-2 antibody (qualitative)
Pregnancy test (urine)	Beta human chorionic gonadotropin (beta-HCG)

To encourage compliance with alcohol restrictions, a breath alcohol test (e.g. AlcoTrue® M, [REDACTED]) will be performed prior to each treatment period, and may be repeated at any time during the trial at the discretion of an investigator or designee. The results will not be included in the CTR.

The laboratory tests listed in Tables 5.2.3: 1 and 5.2.3: 2 will be performed at [REDACTED], with the exception of drug screening and pregnancy tests. These tests will be performed at the trial site using M-10/14-PDT Surestep Multiline test and HCG-K20 test, respectively, or comparable test systems.

Laboratory data will be transmitted electronically from the laboratory to the trial site.

It is the responsibility of the Investigator to evaluate the laboratory reports. Clinically relevant abnormal findings as judged by the Investigator are to be reported as adverse events (please refer to Section 5.2.6).

In case the criteria for hepatic injury are fulfilled, a number of additional measures will be performed (please see Section 5.2.6.1.4).

5.2.4 **Electrocardiogram**

Twelve-lead ECGs (I, II, III, aVR, aVL, aVF, V1 - V6) will be recorded using a computerised electrocardiograph (CardioSoft EKG System, [REDACTED] at the times provided in the [Flow Chart](#).

To achieve a stable heart rate at rest and to assure high quality recordings, the site personnel will be instructed to assure a relaxed and quiet environment, so that all subjects are at complete rest.

Proprietary confidential information © 2022 Boehringer Ingelheim International GmbH or one or more of its affiliated companies

All ECGs will be recorded for a 10 sec duration after subjects have rested for at least 5 min in a supine position. ECG assessment will always precede all other trial procedures scheduled for the same time to avoid compromising ECG quality.

All ECGs will be stored electronically on the Muse CV Cardiology System ([REDACTED]). Electrode placement will be performed according to the method of Wilson, Goldberger and Einthoven.

All locally printed ECGs will be evaluated by the investigator or a designee. Abnormal findings will be reported as AEs (during the trial) or baseline conditions (if identified at the screening visit) if assessed to be clinically relevant by the investigator. Any ECG abnormalities will be carefully monitored and, if necessary, the subject will be removed from the trial and will receive the appropriate medical treatment.

ECGs may be repeated for quality reasons (for instance, due to alternating current artefacts, muscle movements, or electrode dislocation) and the repeated ECG will be used for analysis. Additional (unscheduled) ECGs may be collected by the investigator for safety reasons.

5.2.5 Other safety parameters

5.2.5.1 Suicidality assessment

The C-SSRS is a semi-structured, investigator-rated interview, developed by clinical experts in cooperation with the FDA, assessing both suicidal behaviour and suicidal ideation. It does not give a global score, but provides some categorical and some severity information specifically for behaviour and ideation [\[R08-1147\]](#).

The C-SSRS interview may be administered by any type of physician, psychologist, clinical social worker, mental health counsellor, nurse, or coordinator with C-SSRS training. It has a typical duration of five minutes, and causes only a low burden on subjects. At a minimum, the interview consists of 2 screening questions related to suicidal ideation and 4 related to suicidal behaviour, and may be expanded to up to 17 items in case of positive responses. Free text entries are allowed.

The C-SSRS has been widely used in large multinational CTs. The C-SSRS will be administered at the screening visit (using the 'screening / baseline' version) with the aim to exclude subjects with active moderate or severe symptomatology within a specified time prior to the screening or baseline visit. The life time history of suicidal ideation and behaviour will also be recorded. See Section [10.1](#) for the original English C-SSRS. For this trial, the paper version of the respective German translation will be used.

After the screening visit, the 'since last visit' version is used for the suicidality assessment at the time points indicated in the [Flow Chart](#).

Positive reports are generated for any of the following findings:

Suicidal ideation

- Suicidal ideation with intention to act (type 4)
- Suicidal ideation with specific plan and intent (type 5)

Suicidal behaviour

- Completed suicide
- Suicide attempt
- Interrupted attempt
- Aborted attempt
- Preparatory actions toward imminent suicidal behaviours.

Negative reports of suicidal ideation are defined as reports when there are no indications of the above, i.e. suicidal ideation of type 1-3.

The investigator is to review positive and negative reports for plausibility and clinical relevance. Doubtful reports may be repeated or reports may be validated by a consulting psychiatrist.

If there is a confirmed positive report of suicidal behaviour or suicidal ideation type 4 or 5 after start of trial, the investigator is to immediately interview the subject during the clinic visit, and/or is to consult a psychiatrist. If the positive report is confirmed, appropriate actions for the subject's safety have to be initiated.

For details regarding AE reporting see section [5.2.6.2.4](#)

5.2.6 Assessment of adverse events

5.2.6.1 Definitions of adverse events

5.2.6.1.1 Adverse event

An adverse event (AE) is defined as any untoward medical occurrence in a patient or clinical investigation subject administered a medicinal product and which does not necessarily have to have a causal relationship with this treatment.

An AE can therefore be any unfavourable and unintended sign (including an abnormal laboratory finding), symptom, or disease temporally associated with the use of a medicinal product, whether considered related or not.

The following should also be recorded as an AE in the CRF and BI SAE form (if applicable):

- Worsening of the underlying disease or of other pre-existing conditions
- Changes in vital signs, ECG, physical examination, and laboratory test results, if they are judged clinically relevant by the investigator

If such abnormalities already pre-exist prior to trial inclusion, they will be considered as baseline conditions and should be collected in the eCRF only.

Proprietary confidential information © 2022 Boehringer Ingelheim International GmbH or one or more of its affiliated companies

5.2.6.1.2 Serious adverse event

A serious adverse event (SAE) is defined as any AE which fulfils at least one of the following criteria:

- Results in death
- Is life-threatening, which refers to an event in which the patient was at risk of death at the time of the event; it does not refer to an event that hypothetically might have caused death if more severe
- Requires inpatient hospitalisation, or prolongation of existing hospitalisation
- Results in persistent or significant disability or incapacity
- Is a congenital anomaly/birth defect
- Is deemed serious for any other reason if it is an important medical event when based upon appropriate medical judgment which may jeopardise the patient and may require medical or surgical intervention to prevent one of the other outcomes listed in the above definitions. Examples of such events are intensive treatment in an emergency room or at home for allergic bronchospasm, blood dyscrasias or convulsions that do not result in hospitalisation or development of dependency or abuse

5.2.6.1.3 AEs considered 'Always Serious'

In accordance with the European Medicines Agency initiative on Important Medical Events, Boehringer Ingelheim has set up a list of AEs, which, by their nature, can always be considered to be 'serious' even though they may not have met the criteria of an SAE as defined above.

The latest list of 'Always Serious AEs' can be found in the eDC system, an electronic data capture system which allows the entry of trial data at the trial site. A copy of the latest list of 'Always Serious AEs' will be provided upon request. These events should always be reported as SAEs as described in Section [5.2.6.2](#).

Cancers of new histology must be classified as a serious event regardless of the time since discontinuation of the trial medication and must be reported as described in 5.2.6.2, subsections 'AE Collection' and '**AE reporting to sponsor and timelines**'.

5.2.6.1.4 Adverse events of special interest

The term adverse events of special interest (AESI) relates to any specific AE that has been identified at the project level as being of particular concern for prospective safety monitoring and safety assessment within this trial, e.g. the potential for AEs based on knowledge from other compounds in the same class. AESIs need to be reported to the sponsor's Pharmacovigilance Department within the same timeframe that applies to SAEs, please see Section [5.2.6.2.2](#).

The following are considered as AESIs:

- Potential severe DILI

A potential severe Drug Induced Liver Injury (DILI) that requires follow-up is defined by the following alterations of hepatic laboratory parameters:

- o An elevation of AST (aspartate aminotransferase) and/or ALT (alanine aminotransferase) ≥ 3 -fold ULN combined with an elevation of total bilirubin ≥ 2 -fold ULN measured in the same blood sample, or in samples drawn within 30 days of each other, or
- o Aminotransferase (ALT, and/or AST) elevations ≥ 10 -fold ULN

These lab findings constitute a hepatic injury alert and the subjects showing these lab abnormalities need to be followed up according to the 'DILI checklist' provided via eDC. In case of clinical symptoms of hepatic injury (icterus, unexplained encephalopathy, unexplained coagulopathy, right upper quadrant abdominal pain, etc.) without lab results (ALT, AST, total bilirubin) available, the Investigator should make sure that these parameters are analysed, if necessary in an unscheduled blood test. Should the results meet the criteria of hepatic injury alert, the procedures described in the DILI checklist should be followed.

5.2.6.1.5 Intensity (severity) of AEs

The intensity (severity) of the AE should be judged based on the following:

Mild: Awareness of sign(s) or symptom(s) that is/are easily tolerated

Moderate: Sufficient discomfort to cause interference with usual activity

Severe: Incapacitating or causing inability to work or to perform usual activities

5.2.6.1.6 Causal relationship of AEs

Medical judgment should be used to determine whether there is a reasonable possibility of a causal relationship between the AE and the given trial treatment, considering all relevant factors, including pattern of reaction, temporal relationship, de-challenge or re-challenge, confounding factors such as concomitant medication, concomitant diseases and relevant history.

Arguments that may suggest that there is a reasonable possibility of a causal relationship could be:

- The event is consistent with the known pharmacology of the drug
- The event is known to be caused by or attributed to the drug class
- A plausible time to onset of the event relative to the time of drug exposure
- Evidence that the event is reproducible when the drug is re-introduced
- No medically sound alternative aetiologies that could explain the event (e.g. pre-existing or concomitant diseases, or co-medications)
- The event is typically drug-related and infrequent in the general population not exposed to drugs (e.g. Stevens-Johnson syndrome)

Proprietary confidential information © 2022 Boehringer Ingelheim International GmbH or one or more of its affiliated companies

- An indication of dose-response (i.e. greater effect size if the dose is increased, smaller effect size if dose is reduced)

Arguments that may suggest that there is no reasonable possibility of a causal relationship could be:

- No plausible time to onset of the event relative to the time of drug exposure is evident (e.g. pre-treatment cases, diagnosis of cancer or chronic disease within days / weeks of drug administration; an allergic reaction weeks after discontinuation of the drug concerned)
- Continuation of the event despite the withdrawal of the medication, taking into account the pharmacological properties of the compound (e.g. after 5 half-lives). Of note, this criterion may not be applicable to events whose time course is prolonged despite removing the original trigger
- There is an alternative explanation (e.g. situations where other drugs or underlying diseases appear to provide a more likely explanation for the observed event than the drug concerned)
- Disappearance of the event even though the trial drug treatment continues or remains unchanged

5.2.6.2 Adverse event collection and reporting

5.2.6.2.1 AE collection

Upon enrolment into a trial, the subject's baseline condition is assessed (for instance, by documentation of medical history/concomitant diagnoses), and relevant changes from baseline are noted subsequently.

Subjects will be required to report spontaneously any AEs. In addition, each subject will be regularly assessed by the medical staff throughout the clinical trial and whenever the investigator deems necessary. As a minimum, subjects will be questioned for AEs (and concomitant therapies) at the time points indicated in the [Flow Chart](#). Assessment will be made using non-specific questions such as 'How do you feel?'. Specific questions will be asked wherever necessary in order to more precisely describe an AE.

A carefully written record of all AEs shall be kept by the investigator in charge of the trial. Records of AEs shall include data on the time of onset, end time, intensity of the event, and any treatment or action required for the event and its outcome.

The following must be collected and documented on the appropriate CRF(s) by the investigator:

- From signing the informed consent onwards until an individual subject's end of trial (the End of Study (EoS) visit):
 - All AEs (serious and non-serious) and all AESIs
 - The only exception to this rule are AEs (serious and non-serious) and AESIs in Phase I trials in healthy volunteers, when subjects discontinue from the trial due to screening failures prior to administration of any trial medication. In

these cases, the subjects' data must be collected at trial site but will not be entered in the CRF and will not be reported in the CTR.

- After the individual subject's end of trial:

- The investigator does not need to actively monitor the subject for new AEs but should only report any occurrence of cancer and trial treatment related SAEs and trial treatment related AESIs of which the investigator may become aware of by any means of communication, e.g. phone call. Those AEs should be reported on the BI SAE form (see Section 5.2.6.2.2), but not on the CRF.

5.2.6.2.2 AE reporting to the sponsor and timelines

The Investigator must report SAEs, AESIs, and non-serious AEs which are relevant for the reported SAE or AESI, on the BI SAE form to the sponsor's unique entry point immediately (without undue delay). The country specific reporting process (contact details) will be provided in the ISF. The same timeline applies if follow-up information becomes available. On specific occasions, the Investigator could inform the sponsor upfront via telephone. This does not replace the requirement to complete and send the BI SAE form.

With receipt of any further information to these events, a follow-up SAE form has to be provided. For follow-up information, the same rules and timeline apply as for initial information. All (S)AEs, including those persisting after the individual subject's end of trial, must be followed up until they have resolved, have been sufficiently characterized (e.g. as 'chronic' or 'stable'), or no further information can be obtained.

5.2.6.2.3 Pregnancy

In rare cases, pregnancy might occur in a clinical trial. Once a subject has been enrolled in the clinical trial and has taken trial medication, the investigator must report any drug exposure during pregnancy in a trial participant immediately (within 24 hours) by means of Part A of the Pregnancy Monitoring Form to the sponsor's unique entry point.

The outcome of the pregnancy associated with the drug exposure during pregnancy must be followed up and reported to the sponsor's unique entry point on the Pregnancy Monitoring Form for Clinical Studies (Part B). The ISF will contain the Pregnancy Monitoring Form for Clinical Studies (Part A and Part B).

As pregnancy itself is not to be reported as an AE, in the absence of an accompanying SAE and/or AESI, only the Pregnancy Monitoring Form for Clinical Studies and not the SAE form is to be completed. If there is an SAE and/or AESI associated with the pregnancy, an SAE form must be completed in addition.

5.2.6.2.4 AE reporting from suicidality assessment

All positive reports from C-SSRS suicidality assessment (see section [5.2.5.1](#)), i.e. reports of suicidal ideation type 4 or 5 and all reports of suicidal behaviour must be reported as separate SAEs by the investigator.

Proprietary confidential information © 2022 Boehringer Ingelheim International GmbH or one or more of its affiliated companies

Negative reports (i.e. suicidal ideation type 1, 2 or 3) can be reported as AEs, at the discretion of the investigator. All negative reports should be reviewed by the Investigator for clinical relevance and determination if an AE report is warranted.

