			4:00	12:00	240 mL fluid intake, thereafter lunch ³		X			X		X
			5:00	13:00			X					
			6:00	14:00			X					
			7:00	15:00			X					
			8:00	16:00			X			X		
			10:00	18:00	Dinner ³		X					
			12:00	20:00			X					X
		2	24:00	08:00	Breakfast (voluntary) ³ , discharge from trial site	X ^B	X			X	X	X
			34:00	18:00	Ambulatory visit		X			X		X
		3	48:00	08:00	Ambulatory visit		X					X
		4	72:00	08:00	Ambulatory visit		X					X
		5	96:00	08:00	Ambulatory visit		X					X
		6	120:00	08:00	Ambulatory visit		X					X
		7	144:00	08:00	Ambulatory visit		X					X
		11	240:00	08:00	Ambulatory visit	X ^B	X					X
		14	312:00	08:00	Ambulatory visit		X					X
FU	6	18 to 25			End of study (EoS) examination ⁴	X ^C		X	X	X	X	X

1. Subject must be informed and written informed consent obtained prior to starting any screening procedures. Screening procedures include physical examination, check of vital signs, ECG, safety laboratory (including drug screening and pregnancy test in female subjects), demographics (including determination of body height and weight, smoking status, alcohol history and suicidality assessment), relevant medical history, concomitant therapy and review of inclusion/exclusion criteria. Pharmacogenetic samples will be collected if needed.
2. The time is approximate; the procedure is to be performed and completed within the 3 h prior to drug administration.
3. If several actions are indicated at the same time, the intake of meals will be the last action.
4. At the end of study (synonym for end of trial), the EoS examination includes physical examination, vital signs, ECG, safety laboratory (including pregnancy test in women), recording of AEs, concomitant therapies and suicidality assessment.
5. Only urine drug screening and alcohol breath test as well as pregnancy test in women will be done at this time.
6. AEs and concomitant therapies will be recorded throughout the trial, but will be specifically asked for at the times indicated in the Flow Chart above.
7. Only for T_{fed} and R_{fed}

Proprietary confidential information © 2022 Boehringer Ingelheim International GmbH or one or more of its affiliated companies

8. Suicidality assessment using the Columbia-Suicidal Severity Rating Scale (C-SSRS): 'Screening/Baseline' version at Visit 1, and 'since last visit' version at visit 2-6.
9. Letter A, B and C define different sets of safety laboratory examinations (see Section [5.2.3](#)).

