3.3.4 Withdrawal of subjects from treatment or assessments

Subjects may withdraw or may be removed from trial treatment or may withdraw consent to trial participation as a whole ('withdrawal of consent') with very different implications; please see Sections 3.3.4.1 and [3.3.4.2](#) below.

If a subject is removed from or withdraws from the trial prior to the first administration of trial medication, the data of this subject will not be entered in the case report form (CRF) and will not be reported in the clinical trial report (CTR).

If a subject is removed from or withdraws from the trial after the first administration of trial medication, this will be documented and the reason for discontinuation must be recorded in the CRF; in addition, trial data will be included in the CRF and will be reported in the CTR.

Following removal or withdrawal, a complete end-of-trial examination should be performed. If the discontinuation or withdrawal occurs before the end of the REP (see Section [1.2.2](#), the discontinued subject should, if possible, be questioned for AEs and concomitant therapies at or after the end of the REP, in order to ensure collection of AEs and concomitant therapies throughout the REP, if not contrary to any consent withdrawal of the subject.

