3.3.4.1 Withdrawal from trial treatment

An individual subject will be withdrawn from trial treatment if:

1. The subject wants to withdraw from trial treatment. The subject will be asked to explain the reasons but has the right to refuse to answer
2. The subject has repeatedly shown to be non-compliant with important trial procedures and, in the opinion of both, the investigator and sponsor representative, the safety of the subject cannot be guaranteed as he / she is not willing or able to adhere to the trial requirements in the future.
3. The subject needs to take concomitant medication that interferes with the investigational medicinal product or other trial treatment
4. The subject can no longer receive trial treatment for medical reasons (such as pregnancy, surgery, adverse events (AEs), or diseases). Specifically the subject will not receive further trial treatment if he/she experiences a severe adverse drug reaction (i.e. a severe adverse event judged to be related to trial medication).
5. The subject has an elevation of AST and/or ALT ≥ 3 -fold ULN and an elevation of total bilirubin ≥ 2 -fold ULN (measured in the same blood sample) and/or needs to be followed up according to the DILI checklist provided in the electronic data capture (EDC) system.
6. The subject exhibits serious suicidality, in the clinical judgment of the investigator or according to the following criteria:
 - Any suicidal behaviour (i.e. actual attempt, interrupted attempt, aborted attempt, or preparatory acts or behaviour)

Proprietary confidential information © 2022 Boehringer Ingelheim International GmbH or one or more of its affiliated companies

- Any suicidal ideation of type 2, 3, 4 or 5 in the C-SSRS (i.e. active suicidal thought without method, intent or plan; active suicidal thought with method but without intent or plan; active suicidal thought with method and intent but without specific plan; or active suicidal thought with method, plan and intent)

In addition to these criteria, the investigator may discontinue subjects at any time based on his or her clinical judgment.

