3.3.4.3 Discontinuation of the trial by the sponsor

Boehringer Ingelheim reserves the right to discontinue the trial at any time for any of the following reasons (if reasons 4 and/or 5 are met, the trial should be discontinued immediately):

1. Failure to meet expected enrolment goals overall or at a particular trial site
2. The sponsor decides to discontinue the further development of the investigational products
3. Deviation from GCP, or the CTP impairing the appropriate conduct of the trial
4. New toxicological findings, serious adverse events, or any safety information invalidating the earlier positive benefit-risk-assessment (see Section 3.3.4.1)
5. More than 50% of the subjects show drug-related and clinically relevant adverse events of moderate or severe intensity, or if at least one drug-related serious adverse event is reported

The trial will be at least temporarily halted if two or more severe adverse reactions (i.e. severe adverse events judged to be related to trial medication) are reported.

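### Can a subject be withdrawn for C-SSRS ideation of type 2 or 3 and yet be missing from the adverse event summaries?

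*Protocol*

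**What the plan says.** Criterion 6 of Protocol 3.3.4.1 requires withdrawal from trial treatment when "The subject exhibits serious suicidality, in the clinical judgment of the investigator or according to the following criteria". One of the listed criteria is "Any suicidal ideation of type 2, 3, 4 or 5 in the C-SSRS".

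Protocol 5.2.5.1 sorts C-SSRS reports for a different purpose. Ideation of type 4 or 5 and any suicidal behaviour make a report positive. For the rest, "Negative reports of suicidal ideation are defined as reports when there are no indications of the above, i.e. suicidal ideation of type 1-3". Under Protocol 5.2.6.2.4 every positive report is an SAE. For the others, "Negative reports (i.e. suicidal ideation type 1, 2 or 3) can be reported as AEs, at the discretion of the investigator", and the section adds: "All negative reports should be reviewed by the Investigator for clinical relevance and determination if an AE report is warranted".

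On the analysis side, Protocol 7.2.5 and SAP 7.8.5.3 bring C-SSRS reports into the summaries as AEs recorded under 5.2.6.2.4, and also provide the C-SSRS results as a listing. SAP 7.8.1 lists as other significant AEs the non-serious events that led to action with the study drug. Disposition has its own source. Under Protocol 3.3.4, when a subject leaves after the first dose, "this will be documented and the reason for discontinuation must be recorded in the CRF". SAP 7.8 repeats this for all withdrawals, and SAP Table 6.3: 1 analyses disposition on the treated set.

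**The concern.** The same answer on the C-SSRS carries two labels. Ideation of type 2 or 3 is serious enough to end treatment in one section and is a negative report in another. Nothing in the visible text says that a finding which ends treatment under criterion 6 must also be recorded as an AE.

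An investigator who reads 5.2.6.2.4 literally could therefore withdraw a subject and record no AE. That subject would count as a discontinuation but be absent from the AE tables and from the listing of other significant AEs, since both need an AE record. Prospective suicidality assessment is one of the safety assessments named in Protocol 2.2.2.2, and one subject in 24 is about 4% of the treated set (1/24 = 4.2%). Some of the trial-level rules in Protocol 3.3.4.3 are also framed as adverse events or reactions, for example "The trial will be at least temporarily halted if two or more severe adverse reactions", so an unrecorded finding might seem to escape them.

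**Working it through.** The plan states no figure on this point, so the check sets the rules side by side.

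| C-SSRS finding | Treatment (3.3.4.1, criterion 6) | Report class (5.2.5.1) | AE rule (5.2.6.2.4) |
|---|---|---|---|
| Type 1 | Not a listed trigger | Negative | Investigator decides |
| Type 2 | Withdrawal | Negative | Investigator decides |
| Type 3 | Withdrawal | Negative | Investigator decides |
| Types 4 and 5, suicidal behaviour | Withdrawal | Positive | SAE required |

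The rules part for types 2 and 3 only.

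**Where it could arise.** The Flow Chart places the C-SSRS at screening, on Day -1 of each period and at the end-of-study visit. Day -1 of Visit 2 precedes the first dose, and at Visit 6 a completer has no treatment left to stop. That leaves Day -1 of Visits 3, 4 and 5:

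- 24 subjects × 3 = 72 scheduled assessments, or 20 × 3 = 60 if 4 subjects drop out.
- Washout of at least 17 days, assessment at -12:00: nominally 17 × 24 - 12 = 396 h, or 16.5 days, after the previous dose.

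These figures count questionnaires, not mismatches. A mismatch needs three things together: type 2 or 3 ideation in a healthy volunteer, withdrawal under criterion 6, and a decision that no AE report is warranted.

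**How likely the third step is.** Protocol 5.2.6.1.1 defines an AE broadly enough to include an unfavourable, unintended symptom whatever its cause. Protocol 5.2.6.2.1 requires all AEs, serious or not, to be collected from consent to the end-of-study visit. Protocol 5.2.6.2.4 then requires a review of each negative report for clinical relevance. An investigator who has just stopped treatment because of the finding would find it hard to call it clinically irrelevant.

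**What remains if no AE is recorded.** The C-SSRS result is listed (Protocol 7.2.5, SAP 7.8.5.3), and the withdrawal and its reason are recorded (Protocol 3.3.4, SAP 7.8). The AE tables and the listing of other significant AEs would not show the case.

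**Trial-level rules.** Reason 4 in Protocol 3.3.4.3 extends to safety information of any kind that overturns the benefit-risk assessment, and the end of 3.3.4.1 commits the sponsor to act on new safety information. Neither depends on an AE record. An extra non-serious AE would seldom matter under the other rules: the proportion rule in reason 5 needs more than half the subjects (at least 13 of 24) with drug-related, clinically relevant events of at least moderate intensity, and the temporary halt needs two severe reactions.

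**What a compulsory AE would add.** Under Protocol 7.2.5 an event with onset after the residual effect period goes to follow-up, and SAP 6.1 leaves follow-up out of the Section 15.3 displays. With the C-SSRS taken about 16.5 days after dosing, a compulsory AE could fall there, depending on its onset and on the length of that period, which is not visible. It would then appear in the Section 15.4 displays and the listings, and the Section 15.3 tables could still differ from disposition.

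**The case for a change.** The strongest case for a change is that 5.2.6.2.4 is the specific rule for C-SSRS findings and could be read as overriding the general AE rules. A plan should not depend on which rule an investigator takes to govern, least of all for suicidality. One sentence in each document would settle it, at the price of a little discretion and perhaps one or two extra AE records.

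Part of this stands. The wording does permit the mismatch, and the two labels sit awkwardly together. The override reading is weaker: the discretion in 5.2.6.2.4 comes with a mandatory review of whether an AE report is warranted, so it works as a medical judgement within the general rules. Nor do the documents require AE tables to agree with disposition counts. The visible text is also not the whole instruction: SAP 7.8.1 relies on company standards for AE analysis that are not supplied, and the body of SAP Table 6.1: 2 cannot be read. Whether case report form instructions already tie a withdrawal reason to an AE cannot be judged.

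**Conclusion.** No change to the plan is needed. The text allows a subject withdrawn for type 2 or 3 ideation to have no AE record, but this is a gap that investigators and analysts would fill sensibly. Stopping treatment and automatic SAE reporting serve different purposes, and their thresholds may differ without contradiction. No data would be lost, a single case would stand out among 24 subjects, the sponsor could still act on it, and the pharmacokinetic analysis is untouched.

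The size cannot be put as a rate, because the documents give no expected incidence. The scope is two of five ideation types, at three scheduled assessments per subject, in volunteers screened under exclusion criteria 29 and 30.

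The conclusion assumes that investigators apply the general AE rules alongside 5.2.6.2.4, and that the C-SSRS listing and withdrawal reasons are reported as planned. The differing descriptions in 3.3.4.1, 5.2.5.1 and 5.2.6.2.4 are a minor matter of wording for the sponsor to reconcile; no view is taken on which threshold or label is right.
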